7.9.5.1 Changes in Clinical Laboratory Parameters

Safety laboratory assessments will be carried out locally and evaluated by the investigator to ensure patient safety. The investigator is responsible for reviewing the results of all laboratory tests as they become available. Laboratory tests will be graded according to CTCAE v 4.03.

Laboratory values that fall outside of a clinically accepted reference range or values that differ significantly from previous values must be evaluated by the investigator for clinical significance. The investigator may repeat the laboratory test or request additional tests to verify the results of the original laboratory tests. Abnormal laboratory findings should be reported as an AE if it meets any of the following criteria: 1) causes the patient to discontinue

from study treatment, 2) causes the patient to interrupt the study treatment, or 3) requires intervention.

Generally, Grade 1 laboratory findings need not be reported as AEs unless clinically significant. The investigator will evaluate laboratory findings of \geq Grade 2 or higher classification to determine their clinical significance and if an AE has occurred. Consistent with the CTCAE designation of Grade 3 events as severe or medically significant and Grade 4 events as life-threatening, Grade 3 and Grade 4 laboratory findings should be reported as AEs or SAEs, as appropriate. Grade 2 laboratory findings may be reported as AEs if, in the opinion of the investigator, the event exhibits clinical significance. If clinically relevant abnormal laboratory values are associated with clinical symptom(s), or consistent with a diagnosis, the diagnosis should be reported as the AE (e.g., hemoglobin 9 g/dL in an adult female = anemia). If these clinically relevant abnormal laboratory values do not result in a diagnosis, the test result or finding should be reported as the AE assuming that it does not represent a laboratory error. Repeat testing may be indicated. Such laboratory values should generally be recorded as “increased” or “decreased” (e.g., change from baseline hemoglobin of 13 g/dL to 11 g/dL = hemoglobin decreased). Investigators are required to report any abnormal liver enzyme laboratory values meeting the criteria for potential Hy’s Law as described in [Section 7.9.2.6](#) for immediately reportable event).

7.9.5.2 Overdose

If an event of clinical consequence occurs due to the overdose of either pembrolizumab or margetuximab, an AE needs to be reported to MacroGenics within 24 hours of awareness. All AEs associated with an overdose should be recorded in the eCRF

7.9.5.2.1 Pembrolizumab

No specific information is available on the treatment of overdose of pembrolizumab. In the event of overdose, the participant should be observed closely for signs of toxicity. Appropriate supportive treatment should be provided if clinically indicated.

7.9.5.2.2 Margetuximab

In the event of an overdose, the patient should be closely monitored for potential AEs.

7.9.6 Notification to the Sponsor of Events Requiring Immediate Reporting

IREs, as defined in [Section 7.9.2](#), are events that must be reported immediately to MacroGenics Product Safety or designee within 24 hours of being identified via the IRE reporting form.

Throughout the study, the investigator must immediately complete and fax/email the *Immediately Reportable Event (IRE)* Report Form within 24 hours of identifying the event to MacroGenics Product Safety or designee. The IRE Report Form and IRE Report Form Completion Guidelines are found in the Study Procedures Manual. Additionally, the information regarding IREs needs to be entered into the eCRFs as soon as possible, as outlined in your site contract.

In case of patient or patient partner pregnancy, the MacroGenics Pregnancy Exposure Form must also be completed per Study Procedures. The investigator must attempt to follow the pregnancy to term or termination in order to report on outcome and health status of mother and child. The Pregnancy Exposure Form is found in the Study Procedures Manual.

7.9.7 Emergency Unblinding

Not applicable. This is an open-label study.

7.10 Efficacy, Immunogenicity, Pharmacokinetic, and Pharmacodynamic Assessments

7.10.1 Efficacy Assessments

7.10.1.1 Radiologic Evaluation: Treatment of Patients According to Principles of Immune-Related Response Criteria

Tumor assessments will be obtained at screening using CT and/or MRI scans at time intervals as specified in the [Appendix 1](#) and [Appendix 2](#) (Time and Events Tables). Radiographic disease assessments will occur every 6 weeks (i.e., following 2 cycles of treatment [specifically prior to Cycles 3, 5, 7, etc.]) for the first 24 weeks and then every 12 weeks thereafter until documented progression, initiation of alternative anti-cancer therapy, lost to follow up, withdrawal of informed consent, death, or end of study. Treatment will continue until patients have completed study therapy and required follow-up, experienced disease progression according to irRC, or have been withdrawn from the study (see [Section 4.4](#) and [Section 5.3](#)). At each on-treatment tumor assessment time point, the objective response status will be determined. In the context of the statistical analysis for this trial, objective response determination and the assessment of best overall response (BOR) will be defined using both conventional RECIST 1.1 criteria ([Appendix 7](#)) as well as an adaptation of these criteria, designated as immune-related response criteria (irRC) ([Appendix 8](#)). Patient management decisions, however, will be made solely based on the immune-related response criteria.

For patients who demonstrate acceptable tolerability of treatment with pembrolizumab and margetuximab and achieve an objective response assessment of irCR, irPR or irSD, or unconfirmed clinically stable irPD, therapy may be continued (see [Section 4.4](#) and [Section 5.3](#)).

For patients who are otherwise clinically stable, but have met conventional criteria for PD, therapy may be continued at the discretion of the investigator pending confirmation of progression at the next scheduled tumor assessment. This approach allows for limited treatment of patients beyond the initial radiographic documentation of disease progression, assuming that patients are tolerating therapy adequately, that patients remain otherwise clinically stable despite this initial radiographic evidence of disease progression, and that the investigator feels the patient may still derive benefit from continuation of therapy. Treatment of patients according to irRC principles is supported by well-documented evidence that in some patients treated with T cell directed, immune-modulatory agents, their tumors can evolve to an objective response after an initial period characterized by either apparent radiographic growth of target lesions or the development of new target lesions that would otherwise meet the criteria for disease progression using conventional response criteria ([Appendix 7](#)).

For patients in whom progression is confirmed at the next scheduled tumor assessment, the criteria for immune-related PD (irPD) will have been met, and treatment with margetuximab and pembrolizumab should be discontinued. The patient should be removed from study participation after completion of protocol specified follow-up (see [Section 8.3](#) and [Appendix 1](#) and [Appendix 2](#)). For patients who experience an objective response of immune-related complete response (irCR) or immune-related partial response (irPR), responses will be considered unconfirmed until the response has been documented by a subsequent confirmatory scan obtained no less than 4 weeks after the initial scan demonstrating an objective response.

7.10.1.2 Objective Response and Response Duration

Target and non-target lesions will be designated and evaluated using both conventional RECIST 1.1 criteria ([Appendix 7](#)) and irRC ([Appendix 8](#)) as noted above for the purposes of statistical analysis. Objective responses will be categorized as CR, PR, SD, or PD for conventional RECIST 1.1 criteria and irCR, irPR, irSD, and irPD for the immune-related response criteria. Determination of the objective response rate will be calculated based on the proportion of response evaluable patients achieving CR or PR using the respective criteria, when such responses are confirmed by a subsequent scan obtained at least 28 days after the initial documentation of objective response. Response-evaluable patients will include those patients who have measurable disease and have had a baseline tumor assessment and at least 1 on-treatment tumor assessment (see [Appendix 1](#) and [Appendix 2](#)). Objective responses that are not subsequently documented with a confirmatory CT or MRI scan (e.g., unconfirmed responses) will not be included as an objective response for the purpose of calculating overall objective response rates. Response duration will be calculated from the time of initial response (CR or PR) documentation (in patients who have a subsequent confirmation of objective response) to the time of progressive disease or death, whichever occurs first.

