For patients in whom progression is confirmed at the next scheduled tumor assessment, the criteria for irPD will have been met, and treatment with margetuximab and pembrolizumab should be discontinued. The patient should be removed from study participation after completion of protocol specified follow-up (see [Section 8.3](#), [Appendix 1](#) and [Appendix 2](#)). For patients who experience an objective response of immune-related complete response (irCR) or immune-related partial response (irPR), responses will be considered unconfirmed until the response has been documented by a subsequent confirmatory scan obtained no less than 4 weeks after the initial scan demonstrating an objective response.

Efficacy Assessments:

Objective Response and Response Duration

Target and non-target lesions will be designated and evaluated using both conventional RECIST 1.1 criteria ([Appendix 7](#)) and irRC ([Appendix 8](#)) for the purposes of statistical analysis. Objective responses will be categorized as Complete Response (CR), Partial Response (PR), Stable Disease (SD), or Progressive Disease (PD) for conventional RECIST 1.1 criteria and irCR, irPR, irSD, and irPD for the immune-related response criteria. Determination of the objective response rate will be calculated based on the proportion of response evaluable patients achieving CR or PR using the respective criteria, when such responses are confirmed by a subsequent scan obtained at least 28 days after the initial documentation of objective response. Response evaluable patients will include those patients who have measurable disease and have had a baseline tumor assessment and received one dose of either margetuximab or pembrolizumab (see [Appendix 1](#) and [Appendix 2](#)). Objective responses that are not subsequently documented with a confirmatory CT or MRI scan (e.g., unconfirmed responses) will not be included as an objective response for the purpose of calculating overall objective response rates. Response duration will be calculated from the time of initial response (CR or PR) documentation (in patients who have a subsequent confirmation of objective response) to the time of progressive disease or death, whichever occurs first. A patient's response duration will be censored if at the time of last antitumor assessment response is ongoing.

Progression-free survival (PFS)

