- Determination of mutational burden (on ctDNA determined by Guardant 360 assay), as well as mismatch repair status by microsatellite instability (from pathology reports, when available).
- Determination of PD-L1 tumor cell membranous expression and T cell infiltration (including but not limited to CD4+ and CD8+ T cells) into the tumor bed via IHC staining of paired pre- and on-treatment tumor biopsy specimens.
- Part B only: Determination of HER2 tumor cell membranous expression via IHC staining of pre-treatment and/or on-treatment tumor biopsy specimens.
- Determination of gene expression signatures (i.e., nanostring technology) in tissues, which may be indicative of immunotherapy responses associated with the agents on trial.

Analysis Populations:

Two general populations will be used for the purposes of data analysis - the Safety Population and the Response Evaluable Population as defined below:

- **Safety Population:** All patients who received at least one dose of either margetuximab or pembrolizumab. This population will be used for safety analysis and for analysis of PFS and OS. Patients who receive at least one dose of margetuximab will be included in PK, PD, and immunogenicity analyses.
- **Response Evaluable Population:** All patients who have baseline measurable disease and received at least one dose of either margetuximab or pembrolizumab. This population will be used for analysis of ORR.

Statistical Methods:

Response will be categorized as CR, PR, SD, or PD and evaluated using RECIST 1.1 criteria and as irCR, irPR, irSD, or irPD using the irRC. The ORR will be the proportion of patients in the response evaluable population achieving CR or PR when such responses are confirmed at least 28 days after the initial observation of an objective response. A two-sided 95% exact binomial confidence interval will be calculated around the ORR for each expansion region and also by tumor type.

Response duration will be calculated for responders as the time from initial response (CR or PR) to the time of PD or death. Kaplan-Meier methods will be used to estimate response duration over time and the median response duration. Responders who complete the study without documented PD will be censored at the date of their last tumor assessment.

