8.3 End of Treatment Visit

A list of evaluations to be performed for the End of Treatment visit is provided in [Appendix 1](#) and [Appendix 2](#). Criteria for triggering the End of Treatment visit are specified in [Section 5.3](#). The End of Treatment Visit should be performed after the patient has met off-treatment criteria and End of Study should be noted after patient has been followed for at least 28 days after the last dose of study drug depending on ability to follow the patient and duration and severity of ongoing AEs. It is recognized that certain patients (such as those experiencing progression of disease) may be cared for in facilities other than the participating investigational site, may proceed to receive other cancer therapy, and/or may elect not to return to the investigational site. Therefore, this visit is considered optional, but should be carried out whenever possible.

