9.2.1 Analysis Populations

Two populations will be used for data analysis, the **Safety Population** and the **Response Evaluable Population**, as defined below:

- **Safety Population:** All patients who received at least one dose of either margetuximab or pembrolizumab. This population will be used for safety analysis and for analysis of PFS and OS. Patients who receive at least one dose of margetuximab will be included in PK, PD, and immunogenicity analyses.
- **Response Evaluable Population:** All patients who have baseline measurable disease and received one dose of either margetuximab or pembrolizumab. This population will be used for analysis of ORR.

Patients who withdraw before receiving all protocol-specified treatment before completion of the DLT evaluation period for a reason unrelated to drug toxicity will be considered to have inadequate data to support dose escalation. In this case, replacement patients may be enrolled at the same dose level and schedule as necessary to complete the cohort.

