9.5 Efficacy Endpoints

Response will be categorized as CR, PR, SD, or PD and evaluated using RECIST 1.1 criteria ([Appendix 7](#)) and as irCR, irPR, irSD, or irPD using the irRC ([Appendix 8](#)). The ORR will be the proportion of patients in the response evaluable population achieving CR or PR when such responses are confirmed at least 28 days after the initial observation of an objective response. A two-sided 95% exact binomial confidence interval will be calculated around the ORR for each expansion region and also by tumor type.

Response duration will be calculated for responders as the time from initial response (CR or PR) to the time of PD or death. Kaplan-Meier methods will be used to estimate response duration over time and the median response duration. Responders who complete the study without documented PD will be censored at the date of their last tumor assessment.

PFS will be calculated as the time from the initial infusion of pembrolizumab or margetuximab until documented disease progression or death from any cause. Patients with no PFS event (no disease progression or death from any cause) will be censored at the date of their last tumor assessment. In addition, PFS rates will be calculated at 3 and 6-month time points from the first dose of study drug. Kaplan-Meier methods will be used to estimate PFS over time and the median duration of PFS. The method of Brookmeyer and Crowley ([9](#)) will be used to construct 95% CIs around PFS estimates of the median and other quartiles for each expansion region and also by tumor type.

Incomplete and missing data can complicate interpretation of PFS. [Appendix 5](#) describes the handling of these data for the PFS analysis.

Overall survival is defined as the time from the initial infusion of pembrolizumab or margetuximab to death from any cause. Patients who are alive at last contact will be censored at the date that the patient was last known to be alive. Kaplan-Meier methods will be used to estimate the overall survival function. In addition, OS rate will be calculated at 1 year and 2-year time points from the first dose of study drug.

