Appendix 5 Censoring Rules for PFS

Situation	Date	Outcome
No baseline tumor assessments	Date of first dose	Censored
Death prior to first scheduled tumor assessment	Date of death	Progressed
No post baseline tumor assessments in absence of death prior to first scheduled tumor assessment	Date of first dose	Censored
Documented disease progression	Date of disease progression	Progressed
Initiation of alternative anti-cancer treatments in absence of progression	Date of last tumor assessment prior to initiation of such treatment	Censored
Death or progression immediately after missing two or more consecutive scheduled tumor assessments	Date of last tumor assessment prior to missed assessments	Censored

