### **6.6 Efficacy Endpoint Analyses**

#### **6.6.1 Analyses of Response Endpoints**

The objective response rate (ORR) is estimated as the proportion of patients in the response evaluable population achieving a CR or PR per RECIST v1.1. A two-sided 95% exact binomial CI for ORR will be calculated. In addition, the ORR per irRECIST and its 95% CI will also be calculated.

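### Protocol 7.10.1.2 requires an on-treatment scan for the ORR denominator, contradicting the dose-based definition in the synopsis, Protocol 9.2.1 and SAP 4

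*Protocol*

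**What the plan says.** Five places define who is evaluable for response.

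- **Protocol 7.10.1.2:** measurable disease, and patients must "have had a baseline tumor assessment and at least 1 on-treatment tumor assessment". No dosing condition is given.
- **Protocol synopsis, Objective Response and Response Duration:** the counterpart of 7.10.1.2 and almost identical to it, except that patients must "have had a baseline tumor assessment and received one dose of either margetuximab or pembrolizumab".
- **Protocol synopsis, Analysis Populations:** "All patients who have baseline measurable disease and received at least one dose of either margetuximab or pembrolizumab".
- **Protocol 9.2.1:** "All patients who have baseline measurable disease and received one dose of either margetuximab or pembrolizumab".
- **SAP 4:** the same definition as Protocol 9.2.1.

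The synopsis population list, Protocol 9.2.1 and SAP 4 each assign the ORR analysis to the population they define. The estimator then refers back to it. Protocol 9.5 states: "The ORR will be the proportion of patients in the response evaluable population achieving CR or PR". SAP 6.6.1 uses the "proportion of patients in the response evaluable population achieving a CR or PR per RECIST v1.1". Only confirmed responses count, with confirmation at least 28 days after the first observation.

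**The concern.** Four statements rest on dosing and one rests on having been scanned on treatment. They describe the same group and the same rate. Section 7 introduces itself as a general account of procedures, which makes 7.10.1.2 the outlier. Even so, the paragraph says how ORR is to be calculated, and no rule of precedence is given.

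The two rules part company over patients who leave before the first scan at about week 6. The plan expects some. Appendix 5 has a row for "Death prior to first scheduled tumor assessment" and another for patients with no post-baseline assessment who did not die in that period. Under 7.10.1.2, a patient who dies before the first scan is a PFS event yet disappears from the ORR denominator. An early stopper might still be scanned at the End of Treatment Visit, but Section 8.3 says "this visit is considered optional, but should be carried out whenever possible", and 7.10.1.2 does not say whether such a scan counts as on-treatment.

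At stake is the denominator of a primary efficacy measure in an open-label, single-arm trial. While both definitions stand, the higher of two rates from the same data can claim support in the protocol.

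**Working it through.** **Inputs**

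- Cohort sizes: 30 per region in Part B (60 in all) and up to 25 in Part C (Protocol 9.2).
- Interval: exact binomial, two-sided 95% (Protocol 9.5, SAP 6.6.1).
- Illustrative response counts: 5/30, 10/30 and 6/25 from Protocol Table 7. The pooled Part B example, 12/60, is mine and is not in Table 7.
- Share of treated patients with no on-treatment scan: not given in either document. I assume 0%, 10% and 20%.

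**Step 1: reproduce the plan's own figures.** For x responders of n, the Clopper-Pearson limits are:

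- lower = the 0.025 quantile of Beta(x, n − x + 1)
- upper = the 0.975 quantile of Beta(x + 1, n − x)

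| x/n | Computed 95% CI (%) | Table 7 (%) |
|---|---|---|
| 1/30 | 0.08–17.22 | 0–17 |
| 5/30 | 5.64–34.72 | 5.6–34.7 |
| 10/30 | 17.29–52.81 | 17.3–52.8 |
| 15/30 | 31.3–68.7 | 31.3–68.7 |
| 20/30 | 47.19–82.71 | 47.2–82.7 |
| 1/25 | 0.10–20.35 | 0–20.4 |
| 3/25 | 2.55–31.22 | 2.5–31.2 |
| 6/25 | 9.36–45.13 | 9.4–45.1 |
| 9/25 | 17.97–57.48 | 18.0–57.5 |

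All nine rows agree, apart from rounding.

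**Step 2: direction of the shift.** A confirmed responder needs two post-baseline scans at least 28 days apart. Appendices 7 and 8 count best overall response only from the start to the end of study treatment. A patient with no on-treatment scan therefore cannot be a responder. The scan rule removes m patients from the denominator and none from the numerator:

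ORR under 7.10.1.2 = x/(n − m) = (x/n) × n/(n − m)

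The multiplier is 1.00 at 0%, 1/0.9 = 1.11 at 10% and 1/0.8 = 1.25 at 20%.

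**Step 3: size of the shift.** Responders are held fixed.

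| Case | Dose-based (0% missing) | About 10% missing | 20% missing |
|---|---|---|---|
| 5 of 30 | 16.7% (5.6–34.7) | 5/27 = 18.5% (6.3–38.1) | 5/24 = 20.8% (7.1–42.2) |
| 10 of 30 | 33.3% (17.3–52.8) | 10/27 = 37.0% (19.4–57.6) | 10/24 = 41.7% (22.1–63.4) |
| 6 of 25 | 24.0% (9.4–45.1) | 6/23 = 26.1% (10.2–48.4)* | 6/20 = 30.0% (11.9–54.3) |
| 12 of 60 (illustrative) | 20.0% (10.8–32.3) | 12/54 = 22.2% (12.0–35.6) | 12/48 = 25.0% (13.6–39.6) |

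*2 of 25 removed, that is 8%.

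**Step 4: does other text support the scan rule?** The Part B futility text (synopsis, Protocol 9.2, SAP 3.2 and SAP 6.9) mentions a post-baseline assessment for each of the 15 patients per region. That sets when the look takes place. It does not define the ORR population.

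**The case against.** The strongest reply is that the governing definition is already clear. The sections that define populations agree with one another, they assign ORR to the dose-based population, and the SAP follows them. On that reading 7.10.1.2 is a leftover clause and the bias is nil. Much of this stands: an analysis run from Section 9 and the SAP gives the dose-based ORR. It does not remove the conflict, because 7.10.1.2 itself states how the rate is calculated and nothing subordinates it.

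Three narrower points deserve an answer.

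- **Late responders.** If off-treatment scans do not count as on-treatment, a patient whose response first appears in follow-up could also be excluded. Appendices 7 and 8 close best overall response at the end of treatment, so that patient is not a responder under either rule.
- **No responders.** With zero responders the ORR is 0% either way. This is true, and a trivial exception.
- **The 20% figure.** Entry requires a life expectancy of at least 12 weeks and ECOG 0 or 1, and the first scan falls at about week 6, so the true share may be well below 20%. This is fair. Appendix 5 shows that such patients are foreseen, not how many there will be. The 20% column is an upper bound on an assumption, not a forecast.

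It is also true that PFS and ORR may properly use different populations. The early-death example shows what the scan rule does in practice; it is not a separate error.

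**Conclusion.** The concern holds and should be fixed. Protocol 7.10.1.2 contradicts four other current statements on the denominator of a primary efficacy measure. Where there is at least one responder, any treated patient without an on-treatment scan makes its version of ORR higher. If 7.10.1.2 were followed, 10 of 30 would be reported as 37.0% with 10% of scans missing and 41.7% with 20%, instead of 33.3%. With no missing scans the two definitions coincide.

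These sizes rest on the assumed 0% to 20% range and on reading Appendices 7 and 8 as limiting response to the treatment period. Under the SAP definition the shift is zero, so this is a defect of specification and not a demonstrated bias in the planned analysis.

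**What to change.** In Protocol 7.10.1.2, replace the on-treatment scan condition with the dosing condition as worded in the synopsis Analysis Populations, that is, at least one dose of either drug. A cross-reference to 9.2.1 would serve equally well. Treated patients with measurable disease and no post-baseline scan then stay in the denominator as non-responders, as SAP 4 already implies. If a scan-evaluable ORR is wanted, report it only as a labelled sensitivity analysis.

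The cost is one clause in the protocol. The SAP, the sample size and Table 7 are unchanged. The downside is that the reported ORR may be a few points lower than 7.10.1.2 would give.
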